8.3. Study Procedures Descriptions

Details of the study procedures are described below.

8.3.1. Informed Consent

The nature of the study and its risks and benefits will be explained to the subject (and caregiver as required) by the PI or designee as described in the site-specific ICF approved by the overseeing Institutional Review Board (IRB)/Independent Ethics Committee (IEC) (see [Section 17.3](#)).

8.3.2. Demographics, Medical and Psychiatric History

Demographic data and medical/psychiatric history will be reviewed and documented according to the schedule shown in [Table 1](#).

8.3.3. Drug Testing

A urine drug test for prohibited substances, including benzodiazepines, opioids, amphetamine/methamphetamine, and cocaine, will be performed at the time points specified in [Table 1](#) and [Table 2](#).

8.3.4. Timeline Follow-Back

Alcohol use will be recorded using the Timeline Follow-Back (TLFB) method [[Sobell and Sobell 1992](#)] at the time points specified in [Table 1](#) and [Table 2](#). At each visit where TLFB is to be performed, alcohol use data will be collected for the prior 30-day period.

8.3.5. Concomitant Medication Review

Concomitant medications will be reviewed at every visit. The medications include prescription and nonprescription medications, vitamins, and supplements.

Study staff will record the following data on all medications used by the subject: name, dose, regimen, route of administration, start and stop dates, and the indication for use.

8.3.6. Vital Signs

Vital signs (ie, blood pressure, heart rate, respiratory rate, and oral body temperature) will be assessed at every visit. Blood pressure and heart rate will be measured after the subject has been resting in a seated or supine position for at least 5 minutes.

An effort will be made to consistently use the same arm (preferably the subject's dominant arm) to measure blood pressure and heart rate throughout the study. The blood pressure cuff will be calibrated per study site standard operating procedures (SOP). Automated measurement is preferred, but if performed manually, heart rate will be measured in the brachial artery for at least 30 seconds.

Orthostatic blood pressure and heart rate will be measured according to the schedule shown in [Table 1](#) and [Table 2](#). Orthostatic blood pressure and heart rate will be collected in the following manner:

- Allow subject to be in a supine position for at least 5 minutes
- Measure blood pressure and heart rate
- Have subject stand for 2 minutes
- Measure blood pressure and heart rate

For Part A, orthostatic blood pressure and heart rate measurements will be taken anytime pre-dose and approximately 1 hour post-dose at Visits 3 - 6 and Visit 13 only. At all other dosing visits, routine vital sign assessments will be conducted anytime pre-dose. At all other visits (when no dosing occurs) assessments will be conducted anytime.

For Part B, orthostatic blood pressure and heart rate measurements will be taken pre-dose and approximately 1 hour post-dose at Visits 13 - 16. At all other dosing visits, routine vital sign assessments will be conducted anytime pre-dose. At all other visits (when no dosing occurs) assessments will be conducted anytime.

8.3.7. Physical Examination, Height

A physical examination will be performed according to the schedule shown in [Table 1](#) and [Table 2](#).

Height will be measured at Visit 1 only.

8.3.8. Body Weight and Waist Circumference

Body weight will be measured 3 times at every visit. The median weight will be calculated by an Interactive Web Response System (IWRS) system at Visit 2 and Visit 3 to calculate the change in weight during the first week of olanzapine exposure. At Visit 2, as part of the eligibility assessment, the PI or designee must ensure that the subject's body weight has not changed by greater than 1 kg. Body weight will also be measured prior to discharge from the inpatient stay.

Subjects should be asked to void immediately prior to the body weight measurement. Subjects should be weighed on the same scale for each measurement under the same conditions. Subjects should remove all personal items, such as watches and jewelry, prior to body weight measurement. Subjects should be weighed in hospital gowns with a consistent amount of undergarments for each measurement. Subjects will be weighed 3 times. The median weight will be calculated by an IWRS system as described above at Visit 2 and Visit 3 and entered into an electronic data capture (EDC) system at all other visits.

Waist circumference will be measured according to the schedule shown in [Table 1](#) and [Table 2](#).

8.3.9. 12-Lead Electrocardiogram

A 12-lead ECG will be conducted according to the schedule shown in [Table 1](#) and [Table 2](#). For Part A, ECG will be measured anytime pre-dose and approximately 3 hours post-dose except for Visit 1 and Visit 2 where only 1 ECG will be done. For Visit 2, the ECG should be completed

before dosing. For Visit 6, dosing may be done earlier than normal to accommodate post-dose procedures.

For Part B, ECG will be measured anytime pre-dose and approximately 3 hours post-dose except for Visit 23/ET and Visit 24 where no dosing occurs. For Visit 16, dosing may be done earlier than normal to accommodate post-dose procedure.

8.3.10. Adverse Event Monitoring

AEs will be monitored continuously from the time a subject signs the informed consent document until the completion of the final study visit. AEs and serious adverse events (SAEs) are defined in [Sections 13.2](#) and [13.3](#), respectively. [Section 13.5](#) provides guidance on the monitoring and reporting requirements for AEs. [Section 13.6](#) provides guidance on the reporting requirements for SAEs.

8.3.11. Laboratory Assessments

Blood and urine samples for laboratory assessments will be collected according to the schedule shown in [Table 1](#) and [Table 2](#). Overnight fasting (no eating or drinking for 8 hours before the visit) will be required for labs at Visit 2, Visit 3, Visit 13, and Visit 23/ET. Otherwise, samples will be collected in accordance with the site's usual procedures and analyzed by a central laboratory. Follow-up samples may be obtained for repeat testing as clinically indicated.

Specific hematology, biochemistry, and urinalysis assessments are listed in [Table 3](#). Overnight fasting is required for some visits because fasting glucose and insulin levels (value and absolute change from baseline) will be measured. Otherwise, random glucose and insulin levels will be taken.

Table 3: Clinical Laboratory Assessments

Hematology	Biochemistry	Urinalysis

 • Hematocrit • Hemoglobin • Red blood cell count • Total and differential (absolute) white blood cell count • Platelets 	
 • Sodium • Potassium • Bicarbonate • Glucose¹ • Creatinine • Total protein • Blood urea nitrogen (BUN) • Albumin • Albumin/globulin ratio • Total bilirubin • Alanine transferase (ALT) • Aspartate transferase (AST) • Lactic dehydrogenase (LDH) • Gamma-glutamyl transferase (GGT) • Alkaline phosphatase (ALK-P) • Creatine phosphokinase (CPK) • Insulin¹ • Triglyceride • Total, HDL and LDL cholesterol • Prolactin • Thyroid stimulating hormone (TSH)² 	
 • Color • pH • Specific gravity • Ketones • Protein • Glucose¹ • Bilirubin • Nitrite • Urobilinogen • Occult blood • Cotinine • Microscopic examination of sediment, only if urinalysis dipstick results are abnormal

¹ Requires fasting where indicated on [Table 1](#) and [Table 2](#) (see also [Section 8.3.11](#))

² Assessed at screening only

8.3.11.1. Specialty Laboratory Assessments

In addition to the clinical laboratory assessments listed in Table 3, HbA1c, C-reactive protein, leptin, and carbohydrate deficient transferrin (CDT) will be assessed at select visits, as indicated in [Table 1](#) and [Table 2](#).

A blood sample for pharmacogenetic analyses exploring the relationship between olanzapine-induced weight gain and genotype will be collected according to the schedule in [Table 1](#). This sample will be stored by a third party for up to 10 years after study completion (instructions will be given for shipping to storage facility). Note: This sample should only be taken if subjects have

agreed to it by signing a separate DNA consent form (see [Section 17.3](#)). Subjects may be enrolled in the study without consenting to this procedure, in which case it should not be done.

8.3.11.2. Pregnancy Screening

A pregnancy test will be performed on all women according to the schedule in [Table 1](#) and [Table 2](#). At screening, a serum pregnancy test will be performed. A urine pregnancy test will be performed at all other scheduled time points. A positive result at any time will necessitate the subject's withdrawal from the study.

8.3.12. Pharmacokinetic Assessments

Samidorphan, RDC-9986 (primary metabolite of samidorphan), and olanzapine concentrations will be determined from plasma samples collected according to the schedule in [Table 1](#) and [Table 2](#). The time of last study drug administration and the associated PK blood draw must both be recorded in each subject's appropriate source documents. PK samples will be stored at $-20^{\circ}\text{C} \pm 10^{\circ}\text{C}$.

Pharmacokinetic data may be used to assess compliance with study drug administration and/or included in a subsequent population PK analysis conducted outside of this study.

8.3.13. Clinical Global Impressions-Severity

The PI or designee will complete the CGI-S ([Appendix A](#)) scale at the time points shown in [Table 1](#) and [Table 2](#).

8.3.14. Columbia Suicide Severity Rating Scale

The PI or designee will complete the C-SSRS ([Appendix B](#)) according to the schedule in [Table 1](#) and [Table 2](#). At Screening, the "Baseline" version will be administered, and at all other visits, the "Since Last Visit" version will be administered.

8.3.15. Positive and Negative Syndrome Scale

The PI or designee will complete the PANSS ([Appendix C](#)) according to the schedule in [Table 1](#) and [Table 2](#).

8.3.16. Personal and Social Performance Scale

The PI or designee will complete the 5-point PSP scale ([Appendix D](#)) according to the schedule in [Table 1](#) and [Table 2](#).

8.3.17. Food Craving Inventory

The subject will complete the Food Craving Inventory ([Appendix E](#)) according to the schedule in [Table 1](#) and [Table 2](#).

8.3.18. Impact of Weight on Quality of Life - Lite

The subject will complete the Impact of Weight on Quality of Life - Lite ([Appendix F](#)) questionnaire according to the schedule in [Table 1](#) and [Table 2](#).

8.3.19. Audio Recording

The screening interview and administration of assessments may be recorded using an audio digital pen. A third party may review these recordings for quality assurance and confirmation of subject eligibility.

8.3.20. Olanzapine Administration

Subjects will receive olanzapine for once daily administration according to the schedule in [Table 1](#) and [Table 2](#). The dose will be at the discretion of the PI.

Initiation on olanzapine, including transition from another antipsychotic (as applicable), is a highly individualized process. Formalizing the potential clinical scenarios may pose undue burden and/or risk to subjects. Clinical judgment is essential, and for this reason, the details of this process are left to the discretion of the treating physician, who will follow current clinical practice.

8.3.21. Randomization

After confirming eligibility on Visit 3, and after a 1-week olanzapine lead-in period, subjects will be randomized as outlined in [Section 9.3](#).

8.3.22. Drug Dispensation and Reconciliation

[Section 9](#) provides information related to drug dispensing procedures. The study drug use and storage information will be explained to/reviewed with the subject.

Study drugs include samidorphan and matching placebo tablets, and olanzapine tablets, all for oral administration. Samidorphan is a Schedule II substance, and should be stored, dispensed, and otherwise handled in accordance with the associated regulations.

Olanzapine will be prescribed by the PI and dispensed for oral administration by study staff.

During the inpatient stays, study drug will be dispensed once daily, and the time of administration will be at the discretion of study staff. Time of administration at any visit (inpatient or outpatient) may be adjusted as needed to accommodate post-dose measurements. Before being discharged from each inpatient stay, and at each post-randomization outpatient visit until Visit 23/ET, all subjects will receive blister cards containing samidorphan or placebo for self administration. Subjects will be instructed to take 2 tablets per day from the blister card in addition to their olanzapine tablet(s) once daily in the evening or at bedtime until Visit 23. The subject will take the final samidorphan dose the night before Visit 23. No samidorphan dose will be administered onsite during Visit 23. Olanzapine dosing will continue uninterrupted. Two safety follow-up visits will occur 2 and 4 weeks after Visit 23. Any subject who prematurely discontinues from the study during Part B will be asked to return to the clinic for an ET visit and follow-up visits 2 and 4 weeks after the ET visit.

Subjects will be instructed to keep all unused tablets in their blister card and not to mix tablets between blister cards and bottles.

Subjects will be instructed to return the original containers and any remaining study drug at each subsequent visit. Study drug accountability will be documented as the number of tablets

dispensed, dosed, lost/missing, or remaining. If applicable, the site will discuss noncompliance with the subject.

8.3.23. Emergency Treatment Card

An emergency treatment card will be distributed to each subject prior to discharge at Visit 5. The card will indicate that the subject may be receiving an opioid antagonist and/or olanzapine and will include the PI's contact information, a suggested pain management plan, and information regarding opiate blockade. Subjects will be instructed to keep the emergency treatment card with them at all times. Study personnel will confirm that the subjects have the card in their possession at each study visit. The treatment cards will be collected at Visit 23/ET.

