¹² Full physical examination at screening; brief physical examination at all other scheduled time points

¹³ At screening, the "Baseline" version will be administered, and at all other visits the "Since Last Visit" version will be administered.

¹⁴ During inpatient visits, study drug will be administered by the study staff. Otherwise, study drug will be dispensed for self-administration by the subject

Table 2: Schedule of Assessments (Part B)

	Transition ¹			Active ALKS 3831 Treatment Period									Follow-Up	
	Inpatient Stay			Outpatient Visits										
Study Visit	13 ²	14	15	16	17	18	19	20	21	22	23/ET	24	25	
Study Day:	92 (±2)	93 (±2)	94 (±2)	99 (±1)	106 (±2)	113 (±2)	120 (±2)	134 (±2)	148 (±2)	162 (±2)	176 (±2)	190 (±2)	204 (±2)	
Study Week	13			14	15	16	17	19	21	23	25	27	29	
Weight and Waist Circumference	X	X	X	X	X	X	X	X	X	X	X	X	X	
Pregnancy Test ³	X													
Drug Screens ⁴	X		X	X	X	X	X	X	X	X	X	X	X	
Timeline Follow-Back (TLFB) ⁵	X							X			X		X	
Vital Signs ⁶	X ⁷	X ⁷	X ⁷	X ⁷	X	X	X	X	X	X	X	X	X	
Blood and urine samples for clinical labs ⁸	X		X	X			X		X		X		X	
Hemoglobin A1c, C-reactive protein, leptin	X								X		X		X	
Carbohydrate Deficient Transferrin (CDT)	X							X			X			
Blood samples for PK	X	X	X	X	X	X	X	X	X	X	X			
Physical Examination	X				X						X	X	X	
Electrocardiogram (ECG) ⁹	X		X	X							X	X		
Positive and Negative Syndrome Scale (PANSS)	X			X			X		X		X			
Personal and Social Performance Scale (PSP)	X							X			X			

	Transition ¹			Active ALKS 3831 Treatment Period									Follow-Up	
	Inpatient Stay			Outpatient Visits										
Study Visit	13 ²	14	15	16	17	18	19	20	21	22	23/ET	24	25	
Study Day:	92 (±2)	93 (±2)	94 (±2)	99 (±1)	106 (±2)	113 (±2)	120 (±2)	134 (±2)	148 (±2)	162 (±2)	176 (±2)	190 (±2)	204 (±2)	
Study Week	13			14	15	16	17	19	21	23	25	27	29	
Columbia Suicide Severity Rating Scale (C-SSRS)	X	X	X	X	X	X	X	X	X	X	X	X	X	
Clinical Global Impressions-Severity (CGI S)	X			X			X		X		X			
Food Craving Inventory (FCI)	X			X	X						X		X	
Impact of Weight on Quality of Life – Lite Questionnaire (IWQOL-Lite)	X							X			X			
Interactive Web Response System (IWRS)	X	X	X	X	X	X	X	X	X	X	X			
Olanzapine Dosing ¹⁰	X	X	X	X	X	X	X	X	X	X	X	X	X	
Samidorphan Dosing ¹¹	X	X	X	X	X	X	X	X	X	X				
Collect Emergency Treatment Card											X			
Adverse Event (AE) Monitoring	X	X	X	X	X	X	X	X	X	X	X	X	X	
Concomitant Medication Review	X	X	X	X	X	X	X	X	X	X	X	X	X	

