¹ Transition Visit (end of Part A and beginning of Part B). Assessments at this visit are included in both schedules for convenience.

² All data should be collected pre-dose at Visit 13 except where indicated

³ Urine pregnancy test

⁴ Local drug screen testing via dipstick. The urine drug screen includes benzodiazepines, opioids, amphetamine/methamphetamine, and cocaine. Additional drug tests may be conducted at the discretion of the investigator.

⁵ Alcohol use only

⁶ Orthostatic blood pressure and heart rate measurements will be taken pre-dose and approximately 1 hour post-dose at Visits 13 – 16. At all other dosing visits, routine vital sign assessments will be conducted anytime pre-dose. At all other visits (when no dosing occurs) assessments will be conducted anytime.

⁷ Collect pre-dose and post-dose data.

⁸ An overnight fast is required for labs on Visit 13 and Visit 23/ET

⁹ ECG will be measured anytime pre-dose and approximately 3 hours post-dose except for Visit 23/ET and Visit 24 where no dosing occurs. For Visit 16, dosing may be done earlier than normal to accommodate post-dose procedure.

¹⁰ The subject will take olanzapine uninterrupted through Visit 25

¹¹ The subject will take the final samidorphan dose the night before Visit 23

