8.4.4. Pain Management

Because ALKS 3831 contains samidorphan, a μ -opioid receptor antagonist, patients may experience reduced or ineffective analgesia when taking an opioid analgesic agent concurrently with ALKS 3831, including several days after last dosing of ALKS 3831.

In the event of an emergency, pain management of the subject should include the following:

- Regional analgesia or use of non-opioid analgesics
- If opiate anesthesia or analgesia is required, the subject should be continuously monitored, in an anesthesia care setting, by persons not involved in the conduct of the surgical or diagnostic procedure. The opioid therapy must be provided by individuals specifically trained in the use of anesthetic drugs and the management of the respiratory effects of potent opioids, specifically the establishment and the maintenance of a patent airway and assisted ventilation.
- Close monitoring by appropriately trained personnel in a setting equipped and staffed for cardiopulmonary resuscitation

For subjects requiring emergency opioid analgesics prior to dosing, the study drug should not be administered. If opioid analgesics are required after the study drug has been dosed, it may take several days for opiate sensitivity to be restored, since samidorphan is an opioid antagonist and could interfere with opioid-mediated pain management.

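### Minor safety improvement: the emergency treatment card is collected at Visit 23/ET, for completers the day after the last samidorphan dose, so it may not cover all of the several days of possible opioid blockade

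*Protocol*

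**What the plan says.** Protocol Section 8.3.23 has the card handed out before discharge at Visit 5 and carried at all times. It holds the investigator's contact details, a suggested pain plan and information on opiate blockade, and on exposure: "The card will indicate that the subject may be receiving an opioid antagonist and/or olanzapine". The same section ends its use: "The treatment cards will be collected at Visit 23/ET". Table 2 in Section 8.2 agrees. Its row "Collect Emergency Treatment Card" is marked in the Visit 23/ET column (Day 176) and not at Visit 24 or 25.

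Two footnotes to Table 2 fix the dosing around that visit. For samidorphan: "The subject will take the final samidorphan dose the night before Visit 23". For the other drug: "The subject will take olanzapine uninterrupted through Visit 25".

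Section 8.4.4 says that opioid analgesics may work poorly or not at all while ALKS 3831 is taken, "including several days after last dosing of ALKS 3831". It adds that after a dose "it may take several days for opiate sensitivity to be restored". If opioids are unavoidable, it asks for continuous monitoring in an anesthesia care setting, by people trained in "the management of the respiratory effects of potent opioids". No length is given for the blockade.

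**The concern.** The card lets a clinician who has never met the subject know that an opioid antagonist may be on board. Under the schedule it is taken back about one day after a completer's last samidorphan dose, while the protocol's own pain section expects the effect to last longer. The next scheduled contact is Visit 24, two weeks later, and the available text describes no replacement notice.

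What is at stake is patient safety in an unplanned emergency during those days. Without a written sign of recent exposure, a clinician may not understand why an opioid fails, and may not arrange the monitoring that Section 8.4.4 asks for. Every completer belongs to the group concerned, because all subjects take samidorphan in Part B and former placebo subjects move to the highest dose (Section 8.1.2). Sample size, error rates, endpoints and analyses are untouched.

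**Working it through.** The plan states no figure for this point, so there is none to reproduce. The day counts come from the protocol. The blockade length, completion rate and rate of emergency opioid need are assumptions, because the documents give none of them.

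**Cover under the current schedule, completers**
- Last samidorphan dose: the night before Visit 23, nominally Day 175.
- Card collected: Visit 23, Day 176.
- Cover after the last dose: 176 − 175 = 1 calendar day. The ±2-day visit window does not change this, because the dose is timed relative to the visit.
- Uncovered days = L − 1, where L is the blockade length in days. Assuming L = 3 to 7: 3 − 1 = 2 to 7 − 1 = 6 days. Any L above about 1 day leaves a gap; the assumption sets only its length.

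**Early terminators**
- If the ET visit falls k days after the last samidorphan dose, the gap is L − k, and zero once k reaches L.
- Section 8.1.1 asks Part A terminators to come back immediately, which favors a small k, but no interval is fixed.
- Subjects on placebo who stop in Part A have no blockade and so no gap.

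**Size, completers only**
- Assumed completion 50% to 90% of 280: 0.5 × 280 = 140 to 0.9 × 280 = 252.
- Uncovered person-days: 140 × 2 = 280 to 252 × 6 = 1,512, that is 280/365 = 0.77 to 1,512/365 = 4.14 person-years.
- Assumed emergency opioid need 1% to 10% per person-year: 0.77 × 0.01 = 0.008 to 4.14 × 0.10 = 0.41 occasions.

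**Ceiling, all randomized subjects**
- 280 × 7 = 1,960 person-days; 1,960/365 = 5.37 person-years; × 0.10 = 0.54 occasions.

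**Cover if the card is collected at Visit 24, completers**
- Nominal: 190 − 175 = 15 days.
- With windows: Visit 23 on Day 174 to 178, so last dose on Day 173 to 177; Visit 24 on Day 188 to 192. Minimum 188 − 177 = 11 days, maximum 192 − 173 = 19 days. Even the minimum exceeds the assumed 7 days.
- Time the card outlasts the blockade: nominally 15 − 7 = 8 to 15 − 3 = 12 days; at the window extremes 11 − 7 = 4 to 19 − 3 = 16 days.

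**The case against.** The strongest case against acting has three parts.

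**The hazard is very small.** Less than one occasion of need is expected on any of the assumptions above, and an occasion of need is not a harm. Subjects who expect to need opioids are excluded (Section 7.2, criterion 17), opioid agonists are to be avoided during the study (Section 8.4.1), and each subject has a caregiver or informant in contact several times a week (Section 7.1, criterion 11). This stands, and it makes the point minor. The safeguards do not close the gap, however. The opioid rules address foreseeable use rather than trauma, and a caregiver may not be there when treatment is given.

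**Subjects may be told what they need to know when they leave.** By Visit 23 they have carried the card for months. The consent pages, the card text and the Operational Plan are not available, so exit advice cannot be judged. A reader might infer that subjects leave uninformed. The documents do not support that. They show only that the carried notice is withdrawn, and that the visible text names no replacement.

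**A card kept longer can mislead.** If blockade lasts 3 days, collection at Visit 24 closes a 2-day gap and adds 12 days of outdated warning; if 7 days, it closes 6 and adds 8. The outdated days exceed the closed days at both ends. An undated card could lead a clinician to withhold opioids that would work, or to dose for a blockade that has ended. This stands against simply moving the collection visit. A written last-dose date, with a statement of what it means, limits the problem without removing it.

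A reader might also infer that the two sections contradict each other. They do not: both can be followed exactly as they stand, and the result is a gap in cover.

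**Conclusion.** The gap is real and minor. Following Section 8.3.23 and Table 2 as they stand withdraws a safety notice while Section 8.4.4 says that its reason may persist. The 1 calendar day of cover for completers is a document fact. The 2 to 6 uncovered days rest on an assumed blockade of 3 to 7 days.

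The 0.008 to 0.41 occasions rest on that range together with the assumed completion and need rates. They cover completers only and count opioid need, so they bound harm in that group from above. Including every randomized subject for 7 full days gives about 0.54. A reader might take 0.41 as a forecast of injuries in the whole trial; it is neither a count of injuries nor trial-wide.

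Nor can the gap be assigned to every early terminator. A late ET visit leaves none, and Part A placebo subjects have no blockade. The change is worth making because it is cheap and the possible harm is serious, not because the event is likely.

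**What to change.** 1. In Section 8.3.23 and Table 2, collect the card at Visit 24. Add a footnote that early terminators return it at the follow-up visit two weeks after ET. The footnote is needed because ET shares the Visit 23 column in Table 2 and Table 1 has no ET column.
2. At Visit 23/ET, staff write on the card the date of the last study tablet (samidorphan/placebo) and state that opioid blockade may persist for several days after that date.
3. Do this for all subjects in all four randomized groups, with the same neutral wording, so that the blind is kept.
4. For early terminators, also note whether olanzapine continues. The card's olanzapine statement stays right for completers, who take it through Visit 25, but the protocol does not say that early terminators stay on it.

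The cost is a short amendment with IRB/IEC re-approval (Section 17.1): the sentence in Section 8.3.23, the moved mark, the footnote, and the added lines on the card. No new visit is needed. Some cards will not be recovered, since after ET the follow-up visits are only encouraged (Section 7.3). The card will also outlast the assumed blockade by about 8 to 12 days nominally, which the written date limits. If a carried notice already exists in the exit materials, the sponsor can answer by citing it.
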